### **5.8 PPIE workstream**

The PPIE workstream will run separately from the trial: patients enrolled in the trial will be invited to participate in the PPIE work, but there will not be automatic overlap (i.e. patients will be invited to PPIE, but enrollment in the trial is independent of PPIE engagement, and PPIE engagement does not count towards trial enrollment).

We will engage with brain tumour patients and carers, as well as professionals and the wider public by working with the local neuro-oncology PPI team. We will work with the local clinical team to identify participants, and participation will be by invitation and voluntary participation. All data collected will be anonymised and summarised for thematic analysis and discussion, and to inform the development of the next round of clinical trials.

## **6: PHARMACOVIGILANCE**

### **6.1 Definition of an Adverse Event (AE)**

An AE is any untoward medical occurrence (including deterioration of a pre-existing medical condition) in a subject who is administered any research procedure, which does not necessarily have a causal relationship with this procedure. An AE can therefore be any unfavourable and unintended sign (including an abnormal laboratory finding), symptom or disease temporarily associated with a research procedure, whether or not considered related to the procedure.

### **6.2 Recording of AEs**

PEAR-GLIO Protocol v1.0  
3rd March 2023

AEs will be collected throughout the study, from informed consent through post-surgical care. They will be followed up according to local practice until the event has stabilised or resolved. Any unresolved AEs at the patient's last visit should be followed up for as long as medically indicated, but without further recording in the eCRF. The following details will be collected in the eCRF for each AE: AE term, date of onset, date of resolution, NCI-CTCAE grade maximum intensity, seriousness, investigator causality rating against research procedures, action taken with regards to research procedures and outcome.

### **6.3 Severity of AEs**

Severity is a measure of intensity whereas seriousness is defined by the criteria in section 6.6. Severity will be assessed using the grading scales found in the National Cancer Institute CTCAE version v5.0 (27Nov2017) for all AEs with an assigned NCI-CTCAE term. For those events without assigned NCI-CTCAE grades, the recommendation on page 1 of the NCI-CTCAE that converts mild, moderate and severe into NCI-CTCAE grades should be used. A copy of the NCI-CTCAE version 5.0 can be downloaded from the Cancer Therapy Evaluation Program website (<http://ctep.cancer.gov>).

### **6.4 Causality of AEs**

The Investigator will assess causal relationships between research procedures and each AE.

### **6.5 Abnormal laboratory test results**

Not applicable. Haematological and biochemical parameters will not be assessed throughout the study.

### **6.6 Definition of Serious Adverse Event (SAE)**

An SAE is an AE occurring during any part of the study that meets one or more of the following criteria:

- Is fatal – results in death
  - NOTE: death is an outcome, not an event
- Is life-threatening
  - NOTE: The term 'life threatening' in the definition of 'serious' refers to an event in which the patient was at risk of death at the time of the event; it does not refer to an event which hypothetically might have caused death if it were more serious,
- Requires inpatient hospitalisation or prolongation of existing hospitalisation
  - NOTE: "Hospitalisation" means any unexpected admission to a hospital. It does not usually apply to scheduled admissions that were planned before study inclusion or visits to casualty (without admission). Elective admissions for surgery are also excluded.
- Results in persistent or significant disability/incapacity
- Is a congenital anomaly/birth defect
- Other important medical events

- NOTE: Medical judgement should be exercised in deciding whether an adverse event/reaction is serious in other situations. Important adverse events/reactions that are not immediately life-threatening, or do not result in death or hospitalisation but may jeopardise a subject, or may require intervention to prevent one of the other outcomes listed in the definition above should also be considered serious.

## **6.7 Reporting of SAEs**

Rapid reporting of all SAEs occurring from consent until 3 days after study sample collection must be performed as detailed in the “SAE reporting instructions” within 24 hours of the PI or designee becoming aware of the event. If the investigator becomes aware of safety information that appears to be related to a research procedure involving a subject who participated in the study, even after an individual subject has completed the study, this should also be reported to the Sponsor. All SAEs should be reported to Sponsor using the SAE form and will be reviewed by the CI or designated representative to confirm relatedness and expectedness. Following documented assessment by a delegated investigator, the completed SAE form will be forwarded to the Sponsor by the clinical site within the pre-specified timelines.

All SAEs must be reported to the Sponsor using the PEAR-GLIO SAE form via email and within 24 hours of the site becoming aware of the event.

Please note all events should also be recorded in the relevant sections of the case report forms and patient medical records.

### **6.7.1 Non-reportable events**

Due to the nature of the disease in this study, the following situations that fulfil the definition of an SAE are excluded from recording/reporting on an SAE form. However, they should be recorded on the eCRF and in the medical records.

- Elective hospitalisation and surgery for treatment of cancer or its complications.
- Prolonged hospitalisation for post-surgical complications or post anti-cancer treatment complications.
- Elective hospitalisation to make treatment or procedures easier.
- Elective hospitalisation for pre-existing conditions that have not been exacerbated by trial treatment.

## **6.8 Definition of an Adverse Reaction (AR)**

An AR is any unfavourable and unintended sign (including an abnormal laboratory finding), symptom or disease which temporarily resulted from the administration of any research procedures associated with the study. The expression “reasonable causal relationship” means to convey, in general, that there is evidence or argument to suggest a causal relationship.

## **6.9 Definition of Serious Adverse Reaction (SAR)**

A SAR is an AR that is classed as serious as per the criteria included in section 6.6 of the study protocol.

### **6.10 Definition of Suspected Unexpected Serious Adverse Reaction (SUSAR)**

If an SAE is related to the use of a medical device product or taking part in research procedures, and is not listed in the study protocol as an expected occurrence, then it is a SUSAR.

### **6.11 Reporting of SUSARs**

Research sites will submit SUSARs to the Sponsor. It is the Sponsor's responsibility to report SUSARs to the REC and to disseminate SUSARs to participating sites. Follow-up of patients who have experienced a SUSAR should continue until recovery is complete or the condition has stabilised.

### **6.12 Annual reporting**

The Annual Progress Report (APR) will be sent by the CI to the Sponsor and REC using the NRES template. The APR will be submitted on the anniversary date of the "favourable opinion" letter from the REC. A copy of the APR and an associated correspondence with REC will also be sent to participating sites.

### **6.13 Urgent safety measures**

The CI may take urgent safety measures to ensure the safety and protection of the clinical trial patients from any immediate hazard to their health and safety, in accordance with Regulation 30. The measures should be taken immediately. In this instance, the approval of the REC prior to implementing these safety measures is not required. However, it is the responsibility of the CI to inform the Sponsor and the REC (via telephone for discussion with the medical assessor at the clinical trials unit) of this event **immediately**.

The Sponsor has an obligation to inform the REC in writing within **3 days**, in the form of a substantial amendment. The Sponsor must be sent a copy of the correspondence with regards to this matter.

## **7: STATISTICAL CONSIDERATIONS**

### **7.1 Sample size**

A maximum of fifty (50) evaluable patients will be recruited to this study. This study is not formally powered due to the proof-of-concept nature of the study and broad inclusion criteria. However, the number of samples acquired in this study will enable Pear Bio to conduct analytical validation on the robustness of its precision medicine platform in brain cancer.

### **7.2 Statistical analysis**

PEAR-GLIO Protocol v1.0  
3rd March 2023

### 7.2.1 Primary efficacy analysis

The primary objective of this study does not require patient outcomes. Instead, comparisons will be made to quantify the variability of treatment response within and between patient tumour samples. As these are purely analytical comparisons, they are tied to laboratory results of the Pear Bio test on patient samples. No correlations are made between Pear Bio test results and patient outcomes in the primary analysis.

Comparisons of differentiated *ex vivo* therapeutic response are done on the basis of:

1. Each therapeutic demonstrating its intended mechanism of action based on a before and after biomarker measurement of the tumour/blood sample (e.g., IF assay measuring the level of target protein for a given targeted drug)
2. Computer vision analysis applied to confocal microscopy images of the tumour cell cultures at multiple timepoints, which yields multiple phenotypic metrics of *ex vivo* tumour response, including:
  - a. Cell death
  - b. Cell migration distance/speed (mean, median, 5% most aggressive cells, etc.)
  - c. Immune cell infiltration into the tumour

These analytical measurements are used to conduct the following comparisons:

1. Observing differentiated *ex vivo* treatment response across the therapies/combos tested on each patient's tumour sample (intra-patient sample comparison)
  - a. Ranking of regimen efficacy will be done for each assay metric on a per patient basis to determine agreement/disagreement between assay metrics
  - b. Calculating the range of response to all tested regimens for each assay metric on a per patient basis
2. Observing differentiated *ex vivo* treatment response levels between the cohort of samples collected from patients on a per therapeutic/combo basis (inter-patient sample comparison)
  - a. Grouping of patient samples based on change in biomarker levels on a per regimen basis
  - b. Grouping of patient samples based on *ex vivo* response or resistance at a phenotypic level (quantified by computer vision) on a per regimen basis
  - c. Comparing the general efficacy of the regimens tested across all patient samples using box plots for each phenotypic *ex vivo* tumour response metric of interest
  - d. Comparing the general efficacy of the regimens tested across patient samples using regimen efficacy ranks on each sample and using Kendall's W and Spearman ranked correlation tests to determine whether some regimens consistently outperform others *ex vivo* (on a given metric of interest)

- e. Comparing the general efficacy of the regimens tested across patient samples using Repeated Measures ANOVA for each phenotypic *ex vivo* tumour response metric of interest
- f. Comparing the relative efficacy of any 2 regimens tested across patient samples using a paired T-test for each phenotypic *ex vivo* tumour response metric of interest

The primary objective will be met if there are significant variations in intra-patient and inter-patient sample responses. Due to the heterogeneity of glioma treatment response in the clinic, one regimen is not expected to consistently outperform other options across all patient samples in the laboratory. That could indicate *ex vivo* overperformance due to assay conditions that require adjustment, either in the biology workflow or response vs resistance thresholds, before the assay is used in interventional trials to guide treatment decisions.

### 7.2.2 Secondary efficacy analysis

#### Correlating omics biomarkers to *ex vivo* tumour response

Biomarker expression tied to targeted therapy response (e.g., EGFR to EGFR inhibitors) will be correlated to *ex vivo* tumour response (3D micro-tumour and computer vision platform).

Correlations will be done with various regression models, including:

1. Impact of MGMT methylation on response to treatment
2. Linear regression between continuous biomarkers and *ex vivo* tumour response metrics (e.g., baseline gene expression vs cell viability after treatment with a targeted drug)
3. (Ordinal) Logistic regression correlating low-high, and potentially low-medium-high, biomarker levels against *ex vivo* treatment sensitivity/resistance based on a range of image-based metrics, such as
  - a. Cell viability
  - b. Cell migration speed
  - c. Immune cell infiltration into the tumour

This analysis will be used to establish the concordance/discordance between *ex vivo* responses and biomarkers. However, neither the *ex vivo* responses nor biomarkers will act as a ground truth due to the poor correlation between biomarkers and patient response in patients with malignant brain tumours.. Discordance ( $0 < r < 0.7$ ) will be used to identify patient populations where Pear Bio may be able to predict response differently from known biomarkers. These populations will be considered for future studies to determine whether Pear Bio can accurately predict real-world patient response.

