### **1.2.1 Current management of malignant glioma**

Malignant glioma includes grade 2-4 glioma, and forms the majority of primary brain tumours in adults. Glioma therapy depends on grade and subtype but broadly includes a combination of surgical resection, radiotherapy and chemotherapy.

Optimal treatment of glioblastoma (grade 4 glioma) consists of surgery, chemo-radiotherapy and chemotherapy with Temozolomide (3). For grade 3 astrocytoma, surgery, radiotherapy and adjuvant temozolomide are standard of care (4), and for oligodendroglioma, surgery, radiotherapy and PCV-based chemotherapy are standard of care. At relapse, therapy is typically further chemotherapy, either with the same agents, or previous unused chemotherapy. 3rd-line chemotherapy is poorly defined, but might include carboplatin or irinotecan, and may include bevacizumab.

Combined TMZ & Lomustine may be beneficial in MGMT methylated GBM, but apart from MGMT methylation, IDH mutation and 1p/19q co-deletion - which predict response to chemotherapy in general - there are no biomarkers to predict response to specific therapeutic agents.

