### **1.2.3 Predictive biomarkers of patient response**

The only good predictive biomarkers for glioma are IDH mutation status, 1p/19q codeletion and MGMT methylation. However, these all generally predict for chemotherapy responsiveness, rather than which therapy is best.

Pear Bio's test provides a potential avenue to test single agents and combination therapies prior to treatment selection to guide decision-making.

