### 3.3 Data and tissue collected

	Biospecimens	Data
Required	
 
At least 0.4g of fresh, unfixed, tumour tissue taken from surgery
 
4 x 10mL EDTA vials of matched whole blood
 
	
 
Demographic data (pseudonymised)
 
Redacted pathology reports, including immunohistochemistry tests, molecular pathology and NGS (IDH and MGMT in particular) and further genomic data where available, including methylation profiling
 

		
 
3. Radiology images and reports
 
4. Concomitant medications
 

Collected if available	N/A	
 
1. Blood and liver/kidney function tests at baseline
 
2. Follow-up outcome data, including recurrences
 
3. Follow-up treatment data, including adjuvant therapy regimens
 

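### Section 7.2.2 denies every biomarker reference status, against the protocol's own background on chemotherapy, and its discordance rule lets no result count against the assay

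*Combined protocol and SAP*

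**What the plan says.** **Background.** Section 1.2.3 states: "The only good predictive biomarkers for glioma are IDH mutation status, 1p/19q codeletion and MGMT methylation". It then limits this: the markers indicate responsiveness to chemotherapy broadly and do not say which treatment is best. Section 1.2.1 names the same three markers, "which predict response to chemotherapy in general".

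**Regimens and data.** The standard set in Section 3.4 is a control plus temozolomide, lomustine, the two combined, procarbazine with lomustine, and carboplatin. Section 3.3 makes molecular pathology required data, "IDH and MGMT in particular".

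**Analysis.** Section 7.2.2 opens with targeted agents: "Biomarker expression tied to targeted therapy response (e.g., EGFR to EGFR inhibitors) will be correlated to" ex vivo response. Its first listed item is "Impact of MGMT methylation on response to treatment", with no drug, metric, direction or tumour type given. IDH and 1p/19q are not listed. It then says that neither the assay result "nor biomarkers will act as a ground truth due to the poor correlation between biomarkers and patient response in patients with malignant brain tumours". The band 0 < r < 0.7 is called discordance and is used to find populations in which the platform may predict differently from known biomarkers, and these are considered for future studies.

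**Size.** Section 7.1: "A maximum of fifty (50) evaluable patients will be recruited to this study". It adds: "This study is not formally powered due to the proof-of-concept nature of the study and broad inclusion criteria".

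**The concern.** There are two linked problems.

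First, the reason given for having no reference applies to all biomarkers without exception. It conflicts with the background for chemotherapy, which is the whole of the active standard set. A marker of general chemotherapy response can still serve as a check: samples from methylated tumours should, on the protocol's own account, tend to respond more to chemotherapy.

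Second, the rule attaches a consequence to only one range of r, and that consequence favours the platform. A weak positive correlation is a possible opportunity. A zero or negative one has no reading. One of 0.7 or more is presumably concordance, but nothing follows from it.

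This matters because little else ties the assay to clinical sensitivity. The primary success rule in Section 7.2.1 asks for significant variation within and between samples, which has no external anchor. Section 1.1 rules out formal statistical analysis of patient outcomes. The output of Section 7.2.2 nevertheless helps to choose populations for later trials.

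**Working it through.** The plan gives no power, alpha or effect size, so there is no figure to reproduce. Its one numerical rule, 0 < r < 0.7, can be checked.

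**Inputs from the plan:** the band (Section 7.2.2) and a maximum of 50 evaluable patients (Section 7.1).

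**Assumptions, not in the plan:** MGMT is binary; r is the correlation of MGMT status with a response metric, signed so that positive means methylated is more sensitive; methylated share f = 0.3 to 0.5; MGMT effect d in SD units; 30 or 50 samples with MGMT status.

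**1. No true association.** With t = 0.7·√((n − 2)/(1 − 0.49)) on n − 2 degrees of freedom, P(0 < r < 0.7) = P(T < t) − 0.5.

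| n | r ≤ 0 (no reading) | 0 < r < 0.7 (discordant) | r ≥ 0.7 |
|---|---|---|---|
| 10 | 0.50 | 0.49 | 0.012 |
| 20 | 0.50 | 0.50 | 0.0003 |
| 50 | 0.50 | 0.50 | below 0.0001 |

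**2. A true MGMT effect.** r = d·√(f(1 − f)) / √(1 + f(1 − f)d²).

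- d = 1.0, f = 0.3: 0.458/√1.21 = 0.42.
- d = 1.0, f = 0.5: 0.5/√1.25 = 0.45.
- d needed for r = 0.7: (0.7/√0.51)/√(f(1 − f)) = 0.980/0.5 = 1.96 at f = 0.5, and 0.980/0.458 = 2.14 at f = 0.3.

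Share of 100,000 simulated trials labelled discordant, over f = 0.3 to 0.5:

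| N | d = 1.0 | d = 1.5 |
|---|---|---|
| 50 | over 99% | 89–94% |
| 30 | 97–98% | 80–87% |

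At n = 50, r of about 0.28 is already significant at two-sided 5%, yet it counts as discordance.

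**3. The sign of r.** Section 7.2.1 uses cell death and Section 7.2.2 uses cell viability. With viability as the metric and methylated coded 1, a correct MGMT effect gives r < 0 and falls outside the band altogether.

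**4. What a known-group check could show.** Section 1.2 puts glial tumours at 70% of adult malignant brain tumours. If that held in the study, 0.70 × 50 = 35 gliomas; 25 is an assumed lower case. The half-width of the 95% confidence interval in SD units is t·√(1/n₁ + 1/n₂).

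- 35 gliomas, equal split: 2.035 × √(2/17.5) = 2.035 × 0.338 = 0.69.
- 25 gliomas, equal split: 2.069 × √(2/12.5) = 2.069 × 0.400 = 0.83.

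Two-sided 5% power of the t test, methylated share 40–50%:

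| Gliomas | d = 0.8 | d = 1.0 |
|---|---|---|
| 35 | 61–63% | 80–82% |
| 25 | 47–48% | 65–67% |

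One-sided 5% power at d = 0.8 is 73–75% with 35 gliomas and 60–62% with 25. None of these figures allows for IDH adjustment.

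**The case against.** The other side has several fair points.

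- A reader might infer that MGMT was the plan's positive control and that Section 7.2.2 took the role away. The documents never give it that role. MGMT is only the one specific biomarker with its own analysis item there; EGFR appears as an example, and Section 3.3 singles out IDH as well.
- The background limits these markers to chemotherapy in general. A marker of that kind need not be a ground truth for agent-specific response, and choosing between agents is the platform's purpose. This stands, and it narrows the conflict to chemotherapy. It does not remove it, because the sentence on poor correlation has no exception and MGMT is listed under it.
- A reader might infer that noise always becomes a favourable finding. It does so about half the time per biomarker–metric pair; otherwise it has no reading. The favourable finding is itself only a hypothesis for later study.
- A reader might infer that agreement with MGMT is the only external check. Section 2.2 plans PFS correlations, and Sections 2.3 and 7.2.3 plan other outcome correlations, all informal. Section 7.2.1 has mechanism-of-action measurements and one warning sign, a regimen that consistently outperforms the rest. None of these uses MGMT or gives Section 7.2.2 an unfavourable reading.
- A near-zero MGMT estimate would not prove failure. This stands. The interval is wide, reaching 50 patients depends on the Trial Management Group's review after the first 10, and Section 7.3 allows samples to go to hydrogel and dosing work.

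**Conclusion.** The concern holds in this form. For chemotherapy, the blanket statement in Section 7.2.2 conflicts with Sections 1.2.1 and 1.2.3. The discordance rule gives no result a reading against the assay, and it places an uninformative assay (about half the time) and one that tracks MGMT at 1.0 SD (over 99% of the time at N = 50) in the same category. Followed as written, the rule misleads; it is more than a missing detail.

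The null result at n = 20 to 50 hardly depends on assumptions. The result for a true effect assumes binary MGMT status, a methylated share of 30–50%, and r signed so that a correct effect is positive. The precision and power figures also rest on assumed glioma numbers and effect sizes.

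The documents do not support the stronger reading that the platform would be declared valid on noise, or that a null MGMT result alone would disprove it. As this is a secondary, hypothesis-generating analysis, the change should be made, but the primary objective does not depend on it.

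**What to change.** 1. Reconcile the poor-correlation sentence in Section 7.2.2 with Sections 1.2.1 and 1.2.3. Exempt MGMT, IDH and 1p/19q from the discordance rule for chemotherapy regimens.
2. Specify the existing MGMT item as a known-group check in gliomas: methylated versus unmethylated, for ex vivo response to temozolomide and to lomustine, each relative to the same patient's control culture. Name the metric, state the direction (methylated more sensitive), adjust for IDH where numbers allow, and report the difference with its 95% confidence interval.
3. State the readings in advance. An interval that excludes a meaningful effect in the expected direction, or a reversed effect, weighs against the platform's validity. A wide interval is inconclusive. Neither nominates a population. The SAP must say what size of effect is meaningful.
4. For all other biomarkers, define the sign of r (viability or death) and give readings for r ≤ 0 and r ≥ 0.7.

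**Cost.** This needs SAP wording and one model, on pathology data that Section 3.3 already requires. The sponsor accepts a result that could count against its platform. Because precision is limited, the check should be reported as an estimate with an interval and not as a pass/fail test.

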Confocal microscopy will be conducted daily to collect 3D image data of the cells and track their position and behaviour over time. At the end of the assay, the 3D cell cultures will be fixed or snap-frozen for further 3D immunofluorescence analyses or used for embedding, sectioning and assessment of spatial proteomics. For targeted therapies, RNAseq, IF and proteomics data will be integrated to confirm drug MoA and identify other potential therapeutic targets. Concurrently, 3D image data will be processed through a computer vision pipeline to measure functional metrics of the *ex vivo* 3D cell cultures, including cell viability, tumour culture width and cell migration, both at a bulk tumour level and at a single-cell resolution. A patient report is generated outlining an individual patient sample's response to each therapy tested.

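### The discordance rule in 7.2.2 (0 < r < 0.7) misses part of what it should catch whether r is signed or unsigned, and it cannot be applied to the logistic models

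*Combined protocol and SAP*

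**What the plan says.** Section 7.2.2 relates omics biomarkers to *ex vivo* response: "Correlations will be done with various regression models". Three items follow:

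1. "Impact of MGMT methylation on response to treatment", with no model form given.
2. Linear regression for continuous biomarkers, with the example "baseline gene expression vs cell viability after treatment with a targeted drug".
3. Binary or ordinal logistic regression of grouped biomarker levels against sensitivity or resistance, with viability, migration speed and immune infiltration as the metrics.

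The purpose is then stated: "This analysis will be used to establish the concordance/discordance between" *ex vivo* responses and biomarkers, with neither treated as the truth. The decision rule is "Discordance ( $0 < r < 0.7$ ) will be used to identify patient populations" in which the assay might predict response differently from known biomarkers. The consequence is that "These populations will be considered for future studies".

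The symbol r is not defined there or anywhere else. The only correlation coefficient named in the document is in 7.2.1, for regimen ranks: "Spearman ranked correlation tests to determine whether some regimens consistently outperform others". Response is measured in both directions. Section 7.2.1 lists cell death, which rises with response. Section 3.4 describes the image metrics as "including cell viability, tumour culture width and cell migration", and 7.2.2 also uses viability, which falls with response. No common orientation is set, and no cut-off for concordance is written down.

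**The concern.** The rule is meant to pick out biomarker-metric pairs that do not agree. A range open at 0 and at 0.7 can be read in two ways, and each leaves out something a discordance rule should catch.

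- **Signed r.** Zero and negative values have no label, although they are further from agreement than any value inside the range. Reversing the direction of the metric also reverses the sign of r.
- **Unsigned r** (an absolute value, or the multiple R of a regression). Direction is lost, so strong opposition looks the same as strong agreement and falls on the implied concordant side.

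A separate gap is that item 3 produces odds ratios, and the rule has no direct meaning for them.

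At stake is which populations are carried forward as candidates for later studies. If the reading is settled after the data are seen, so is part of that selection.

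**Working it through.** **Inputs.** From the documents: the range 0 < r < 0.7 (7.2.2) and a maximum of 50 evaluable patients (7.1). The number of samples per biomarker-metric pair is not given, and the additional drugs, targeted ones among them, are tested only if cells suffice (3.4). Assumed: n = 5, 10, 20, 50; bivariate normality; true correlations of 0, 0.3, 0.8 and -0.8. *Oriented* means coded so that a positive r is agreement with the expected direction. The plan derives no figure here to reproduce; 0.7 is simply a cut-off.

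**Step 1: true correlation 0 (exact).** Let t = r√(n − 2)/√(1 − r²), with n − 2 degrees of freedom. At r = 0.7, t = 0.7√(n − 2)/√0.51. Write F for the probability of falling below that t. By symmetry:

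- signed rule, no label: P(r ≤ 0) = 0.5 at every n;
- signed rule, flagged: F − 0.5;
- unsigned rule, flagged: 2F − 1;
- oriented r < 0.7, flagged: F.

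| n | t at 0.7 | F | signed: flagged | signed: no label | unsigned: flagged | oriented r < 0.7: flagged |
|---|---|---|---|---|---|---|
| 5 | 1.698 | 0.906 | 41% | 50% | 81% | 91% |
| 10 | 2.772 | 0.988 | 49% | 50% | 98% | 99% |
| 20 | 4.159 | 0.9997 | 50% | 50% | 99.9% | 100% |
| 50 | 6.791 | 1.000 | 50% | 50% | 100% | 100% |

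With a signed r, half of all unrelated pairs go unlabelled on the sign of noise. With an unsigned r, the rule handles them as intended.

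**Step 2: signed r and coding (simulation, 400,000 samples per n).** Take a true correlation of 0.3 with death, and suppose viability = 100% − death, so that r changes sign.

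| n | flagged, scored as death | flagged, same samples scored as viability |
|---|---|---|
| 5 | 51% | 25% |
| 10 | 74% | 18% |
| 20 | 89% | 9% |
| 50 | 98% | 2% |

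With an unsigned r the two columns would be identical.

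**Step 3: unsigned r and strong opposition (same simulation).** True oriented correlation −0.8:

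| n | unsigned: outside discordance | oriented r < 0.7: flagged |
|---|---|---|
| 5 | 74% | 99.8% |
| 10 | 78% | at least 99.8% |
| 20 | 86% | at least 99.8% |
| 50 | 95% | at least 99.8% |

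**Step 4: which coefficient.** In one constructed data set with n = 50 and Pearson r = 0.800, Spearman is 0.822, and neither is flagged. Kendall's tau is 0.634. After a median split of the biomarker, the point-biserial coefficient is 0.663; after splitting both variables, phi is 0.680. All three would be flagged. A logistic fit to the split data gives a log odds ratio of 3.32 (odds ratio 27.6), which cannot be compared with 0.7. This is an illustration, not an estimate for this study.

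**The case against.** The best defence is that r is meant as a magnitude. A range that starts at 0 and follows a list of regression models reads naturally that way. The plan's own example supports it: if high target expression goes with sensitivity, expression against viability should give a negative r, so a signed rule would leave the expected result with no label at all. On the unsigned reading, unrelated pairs are flagged and coding changes nothing. It can also be said that strong opposition still means the biomarker largely determines the assay reading, so leaving it out is a matter of judgement.

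Much of this stands. A reader might infer that the label of any pair turns on how response is scored. The documents do not support that: it follows only if r is signed, and 7.2.2 itself lists viability, with death appearing in 7.2.1. Nothing says a 7.2.2 result would be rescored. Nor does it add evidence to say that the signed flag differs between codings in 75% to 100% of samples at a true 0.3. That figure is just P(|r| < 0.7), because reversing a sign always moves such an r across zero.

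What remains is that neither reading is stated and neither does the whole job. Opposition is the plainest case of an assay pointing a different way from a biomarker, which is what the rule is meant to find. A default reading of r as Pearson's from item 2 settles neither the sign nor the treatment of items 1 and 3.

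**Conclusion.** The rule needs correcting, and the issue is minor. If r is signed, 50% of unrelated pairs get no label at any n and coding decides the label. If r is unsigned, the failure is confined to strong opposition: 74% to 95% of samples fall outside discordance at a true oriented −0.8. On either reading the cut-off has no direct meaning for the logistic models.

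The percentages rest on assumed sample sizes, assumed true correlations and bivariate normality; none of these is in the documents. That a signed range leaves zero and negative values unlabelled, and that an unsigned one cannot see direction, needs no assumption.

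A reader might go further and conclude that the study's findings are at risk. The documents do not support that. The analysis sits outside the primary objective, section 7.1 says the study is not formally powered, and flagged populations are only considered for later work. Patient care is not touched.

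**What to change.** In 7.2.2:

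- Name one signed coefficient, for example Pearson r for item 2.
- Score every response metric so that higher means more response, and fix each biomarker's expected direction in a short table before analysis. Where no direction can be stated in advance, report r without a label.
- Replace the range with oriented r < 0.7, including zero and negative values, as discordance, and state concordance as oriented r ≥ 0.7. This keeps the plan's own cut-off.
- Report each r with its 95% interval and n.
- For a binary biomarker such as MGMT status, which sections 1.2.1 and 1.2.3 treat as established, either use the oriented point-biserial coefficient against the continuous metric, named as such, or report the effect estimate with its interval.
- Do not apply the r cut-off to logistic odds ratios.

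The cost is a text change and the table of directions; no new data are needed. Some pairs, possibly those with migration or immune infiltration, may stay unlabelled. The label also remains imprecise at small n: a true oriented r of 0.8 would still be called discordant in 27%, 22%, 14% and 5% of samples at n = 5, 10, 20 and 50. This is why the interval and n should accompany each r.
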